4. STUDY OBJECTIVES

4.1 **Primary Objective**

The primary objective of this study is to characterize the safety and tolerability of LY3819253 after intravenous (IV) infusion.

4.2 Secondary Objectives

The secondary objectives of this study are:

- To characterize the PK of LY3819253 after IV infusion.
- To characterize the PD of LY3819253 after IV infusion.

4.3 Exploratory Objective

The exploratory objectives of this study are:

• To characterize the participant's clinical status.

- Characterize the pharmacodynamics of LY3819253 after intravenous infusion.
- Characterize emergence of viral resistance to LY3819253.

5. STUDY ENDPOINTS

5.1 **Primary Endpoint**

• Safety assessments such as adverse events (AEs) and serious AEs (SAEs).

5.2 Secondary Endpoints

- LY3819253 mean concentration on Day 29.
- Change from baseline in severe acute respiratory syndrome coronavirus 2 (SARS-CoV-2) viral load (Days 7, 11, 15, and 22).
- SARS-CoV-2 viral load area under the concentration versus time curve (AUC).
- Time to SARS-CoV-2 clearance.

5.3 Exploratory Endpoints

- Duration (days) of hospitalization.
- Proportion (percentage) of participants admitted to intensive care unit (ICU).
- Proportion (percentage) of participants requiring mechanical ventilation.
- Score using the National Institute of Allergy and Infectious Diseases (NIAID) and World Health Organization (WHO) ordinal scale or live discharge from hospital at pre-specified time points.
- National Early Warning Score (NEWS2) score at pre-specified time points.
- Proportion (percentage) of participants with at least a 2-point improvement on the NIAID and WHO ordinal scale or live discharge from hospital at pre-specified time points.
- NEWS2 score at pre-specified time points.
- Proportion (percentage) of participants with any worsening on the NIAID ordinal scale from baseline to Day 15.
- Proportion of participants that achieve SARS-CoV-2 clearance (Days 7, 11, 15, 22).
- Emergence of viral resistance to LY3819253 from baseline to Day 29.

6. STUDY DESIGN

Study PYAA is a Phase 1, double-blind, sponsor unblinded, randomized, placebo-controlled, single-ascending dose study in participants hospitalized for COVID-19.

The study will comprise up to 4 dose cohorts. Cohorts 1-3 will compromise at least 8 participants:

- 6 randomized to LY3819253 and
- 2 randomized to placebo.

Sentinel dosing will be used in any dose cohort that represents a dose increase from the preceding cohort. The first 2 participants in each cohort will be randomized 1:1 to LY3819253 and placebo.

Safety and tolerability will be reviewed for sentinel participants up to 24 hours after dosing. The investigator and the Lilly sponsor team are responsible for determining if safety and tolerability is acceptable to continue with dosing subsequent participants. Subsequent participants will be randomized to the remaining treatment allocations, 5 to LY3819253 and 1 to placebo.

The decision to dose the next cohort will be made when all participants from the previous cohort have been dosed and safety data is assessed for at least 4 days after the IV infusion by the investigator(s) and Lilly sponsor team in consultation with an independent safety assessment committee (ISAC).

Cohort 4 may be initiated, at the discretion of the sponsor team, if more data is needed to inform

Figure 1 - Sequential single ascending dose schema of study J2W-MC-PYAA

7. TREATMENTS

Cohort	Study Treatment Name*	Treatment order in TFL
All	Pooled placebo IV	1
1	700 mg LY3819253 IV	2
2	2800 mg LY3819253 IV	3
3	7000 mg LY3819253 IV	4
4 (optional)	TBD mg LY3819253 IV	5

The following is a list of the study treatment abbreviations that will be used in the TFLs.

Abbreviations: IV = intravenous; TBD = to be determined.

* Planned doses presented - the actual dose administered will be displayed in the TFLs.

8. SAMPLE SIZE JUSTIFICATION

For Cohorts 1-3, approximately 24 participants will be randomized to receive one of three dose levels of LY3819253 or placebo. Additional participants may be required to ensure a minimum of 8 participants in each cohort complete 7 days of study assessments. Up to a maximum of 3 additional participants per cohort may be added.

Participant viral loads over time were simulated using a representative PK/PD model to enable a Monte Carlo assessment of the power of the trial to detect a 30% treatment difference in mean AUC (28 day) of viral load. This assessment revealed greater than 90% probability of meeting the following Bayesian critical success factor:

Pr ((mean AUC_{PL} – mean AUC_{LY})/ mean AUC_{PL} > 0.3) > 0.60

PL = placebo, LY = LY3819253

Additionally, the anticipated 6 participants per treatment provides greater than 80% probability (within each treatment arm) of observing safety events of reasonable prevalence (that is, at least 25%) to support the primary objective of safety assessment.

For the optional Cohort 4, up to 100 participants may be randomized in an approximate 1:1 ratio to receive either LY3819253 or placebo. The overall numbers of participants randomized to LY3819253 and placebo in this study will provide 60% power to detect a reduction in the rate of clinical worsening from 22% to 9% (one-sided alpha=0.05). Clinical worsening is defined as the proportion (percentage) of participants with any worsening on the NIAID ordinal scale from baseline to Day 15.

A participant is only allowed to receive one IV infusion in one cohort.

9. DEFINITION OF ANALYSIS POPULATIONS

The "Entered" population will consist of all participants who sign the informed consent form.

The "Safety" population will consist of all participants randomly assigned and who received study intervention (either placebo or LY3819253). Participants will be analyzed according to the intervention they actually received.

The "Pharmacokinetic" population will consist of all randomized participants who received study intervention (LY3819253) and have at least one evaluable PK sample. Participants will be analyzed according to the intervention they actually received.

The "Pharmacodynamic" population will consist of all randomized participants who received study intervention (either placebo or LY3819253) and provided at least one post-baseline measure for the relevant endpoint. Participants will be analyzed according to the intervention they actually received.

All protocol deviations that occur during the study will be considered for their severity/impact and will be taken into consideration when participants are assigned to analysis populations.

10. STATISTICAL METHODOLOGY

10.1 General

Data listings will be provided for all data that is databased. Summary statistics and statistical analysis will only be presented for data where detailed in this SAP. For continuous data, summary statistics will include the arithmetic mean, arithmetic standard deviation (SD), median, min, max and N; for log-normal data (e.g. the PK parameters: AUCs and maximum observed drug concentration $[C_{max}]$) the geometric mean and geometric coefficient of variation (CV%) will also be presented. For categorical and ordinal data, frequency count and percentages will be presented. Data listings will be provided for all participants up to the point of withdrawal, with any participants excluded from the relevant population highlighted. Summary statistics and statistical analyses will generally only be performed for participants included in the relevant analysis population. For the calculation of summary statistics and statistical analysis, unrounded data will be used.

Mean change from baseline is the mean of all individual participants' change from baseline values. Each individual change from baseline will be calculated by subtracting the individual participant's baseline value from the value at the timepoint. The individual participant's change from baseline values will be used to calculate the mean change from baseline using a SAS procedure such as Proc Univariate.

Data analysis will be performed using SAS[®] Version 9.4 or greater.

10.2 Demographics and Participant Disposition

Participant disposition will be summarized and listed. The demographic variables age, sex, race, ethnicity, country of enrolment, site ID, body weight, height, body mass index and saturation of peripheral oxygen (SpO2) will be summarized and listed. All other demographic variables will be listed only. Additional clinic meaningful parameters may be added if deemed necessary.

10.3 Pharmacokinetic Assessment

10.3.1 Pharmacokinetic Analysis

PK analysis will be the responsibility of the Eli Lilly PK/PD group prior to database lock.

PK parameter estimates for LY3819253 will be calculated using standard noncompartmental methods of analysis.

The primary parameters for analysis will be geometric mean of concentration on Day 29. Other noncompartmental parameters, such as half-life, AUC from time 0 to infinity (AUC[0- ∞]), AUC from time 0 to Day 29 (AUC[0-D29]), C_{max}, clearance, and volume of distribution may be reported.

Additional population PK model-based analyses may be performed.

Noncompartmental methods applied with a validated software program (Phoenix WinNonlin Version 8.1 or later) to the serum concentrations of LY3819253 will be used to determine the following PK parameters, when possible:

Parameter	Units ^a	Definition
AUC(0-D29)	µg.h/mL	Area under the concentration versus time curve from time zero to time t, where t is Day 29
$AUC(0-t_{last})$	µg.h/mL	Area under the concentration versus time curve from time zero to time t, where t is the last time point with a measurable concentration
$AUC(0-\infty)$	μg.h/mL	Area under the concentration versus time curve from time zero to infinity
%AUC(t_{last} -∞)	%	Percentage of AUC($0-\infty$) extrapolated
t _{last}		Time of the last observed drug concentration
C _{max}	µg/mL	Maximum observed drug concentration
C _{D29}	μg/mL	Observed drug concentration on Day 29
t _{max}	h	Time of maximum observed drug concentration
$t_{\frac{1}{2}}$	h	Half-life associated with the terminal rate constant (λ_z) in non-compartmental analysis
CL	L/h	Total body clearance of drug calculated
Vz	L	Volume of distribution during the terminal phase
V _{ss}	L	Volume of distribution at steady state

^a Units of source LY3819253 serum concentration data will be ng/mL, to one decimal place.

Additional PK parameters may be calculated, as appropriate.

The software and version used for the final analyses will be specified in the CSR. Any exceptions or special handling of data will be clearly documented within the final study report.

Formatting of tables, figures and abbreviations will follow the Eli Lilly Global PK/PD/TS Tool: NON-COMPARTMENTAL PHARMACOKINETIC STYLE GUIDE. The version of the tool effective at the time of PK analysis will be followed.

General PK Parameter Rules

- Actual sampling times will be used in the final analyses of individual PK parameters, except for non-bolus pre-dose sampling times which will be set to zero.
- C_{max} and time of maximum observed drug concentration (t_{max}) will be reported from observed values. If C_{max} occurs at more than one time point, t_{max} will be assigned to the first occurrence of C_{max} .
- AUC parameters will be calculated using a combination of the linear and logarithmic trapezoidal methods (linear-log trapezoidal rule). The linear trapezoidal method will be applied up to t_{max} and then the logarithmic trapezoidal method will be used after t_{max}. The minimum requirement for the calculation of AUC will be the inclusion of at least three consecutive serum concentrations above the lower limit of quantification, with at least one of these concentrations following C_{max}.
- AUC(0-∞) values where the percentage of the total area extrapolated is more than 20% will be flagged. Any AUC(0-∞) value excluded from summary statistics will be noted in the footnote of the summary table.
- Half-life $(t_{\frac{1}{2}})$ will be calculated, when appropriate, based on the apparent terminal loglinear portion of the concentration-time curve. The start of the terminal elimination phase for each participant will be defined by visual inspection and generally will be the first point at which there is no systematic deviation from the log-linear decline in serum concentrations. Half-life will only be calculated when a reliable estimate for this parameter can be obtained comprising of at least 3 data points. If $t_{\frac{1}{2}}$ is estimated over a time window of less than 2 half-lives, the values will be flagged in the data listings. Any $t_{\frac{1}{2}}$ value excluded from summary statistics will be documented in the footnote of the summary table.
- A uniform weighting scheme will be used in the regression analysis of the terminal loglinear portion of the concentration-time curve.
- The parameters based on predicted last quantifiable drug concentration will be reported (except in bioequivalence and bioavailability studies, where only the observed parameters will be reported).

Individual PK Parameter Rules

• Only quantifiable concentrations will be used to calculate PK parameters with the exception of special handling of certain concentrations reported below the lower limit of quantification (BQL). Serum concentrations reported as BQL will be set to a value of zero when all of the following conditions are met:

- The compound is non-endogenous.
- The samples are from the initial dose period for a patient or from a subsequent dose period following a suitable wash-out period.
- The time points occur before the first quantifiable concentration.
- All other BQL concentrations that do not meet the above criteria will be set to missing.
- Also, where two or more consecutive concentrations are BQL towards the end of a profile, the profile will be deemed to have terminated and therefore any further quantifiable concentrations will be set to missing for the calculation of the PK parameters unless it is considered to be a true characteristic of the profile of the drug.

Individual Concentration vs. Time Profiles

- Individual concentrations will be plotted utilizing actual sampling times.
- The terminal point selections will be indicated on a semi-logarithmic plot.

Average Concentration vs. Time Profiles

- The average concentration profiles will be graphed using scheduled (nominal) sampling times.
- The average concentration profiles will be graphed using arithmetic average concentrations.
- The pre-dose average concentration for single-dose data from non-endogenous compounds will be set to zero. Otherwise, only quantifiable concentrations will be used to calculate average concentrations.
- Concentrations at a sampling time exceeding the sampling time window specified in the protocol, or $\pm 10\%$, will be excluded from the average concentration profiles.
- Concentrations excluded from the mean calculation will be documented in the final study report.
- A concentration average will be plotted for a given sampling time only if 2/3 of the individual data at the time point have quantifiable measurements that are within the sampling time window specified in the protocol or ± 10%. An average concentration estimated with less than 2/3 but more than 3 data points may be displayed on the mean concentration plot if determined to be appropriate and will be documented within the final study report.

Treatment of Outliers during Pharmacokinetic Analysis

Application of this procedure to all PK analyses is not a requirement. Rather, this procedure provides justification for exclusion of data when scientifically appropriate. This procedure describes the methodology for identifying an individual value as an outlier for potential exclusion, but does not require that the value be excluded from analysis. The following methodology will not be used to exclude complete profiles from analysis.

Data within an Individual Profile

A value within an individual profile may be excluded from analysis if any of the following criteria are met:

- For PK profiles during multiple dosing, the concentration of the pre-dose sample exceeds all measured concentrations for that individual in the subsequent post-dose samples.
- For PK profiles during single dosing of non-endogenous compounds, the concentration in a pre-dose sample is quantifiable.
- For any questionable datum that does not satisfy the above criteria, the profile will be evaluated and results reported with and without the suspected datum.

Data between Individual Profiles

- 1. If n<6, then the dataset is too small to conduct a reliable range test. Data will be analyzed with and without the atypical value, and both sets of results will be reported.
- 2. If $n \ge 6$, then an objective outlier test will be used to compare the atypical value to other values included in that calculation:
 - a. Transform all values in the calculation to the logarithmic domain.
 - b. Find the most extreme value from the arithmetic mean of the log transformed values and exclude that value from the dataset.
 - c. Calculate the lower and upper bounds of the range defined by the arithmetic mean ± 3 *SD of the remaining log-transformed values.
 - d. If the extreme value is within the range of arithmetic mean ± 3 *SD, then it is not an outlier and will be retained in the dataset.
 - e. If the extreme value is outside the range of arithmetic mean ± 3 *SD, then it is an outlier and will be excluded from analysis.

If the remaining dataset contains another atypical datum suspected to be an outlier and $n \ge 6$ following the exclusion, then repeat step 2 above. This evaluation may be repeated as many times as necessary, excluding only one suspected outlier in each iteration, until all data remaining in the dataset fall within the range of arithmetic mean ± 3 *SD of the log-transformed values.

Reporting of Excluded Values

Individual values excluded as outliers will be documented in the final report. Approval of the final report will connote approval of the exclusion.

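### SAP 10.3.1: for six or more values the PK outlier rule orders an exclusion that its own preamble does not require, and asks for no parallel result, although a flag at the planned group size is weak evidence

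*SAP*

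**What the plan says.** The rule is in SAP 10.3.1, under the treatment of outliers.

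- **Preamble.** "Application of this procedure to all PK analyses is not a requirement". Instead, "this procedure provides justification for exclusion of data when scientifically appropriate". The method identifies a value for possible exclusion but "does not require that the value be excluded from analysis". It adds: "The following methodology will not be used to exclude complete profiles from analysis".
- **Within one profile.** For a questionable value that meets neither listed criterion, "the profile will be evaluated and results reported with and without the suspected datum".
- **Between profiles, n < 6.** The SAP calls the dataset too small for a reliable range test. "Data will be analyzed with and without the atypical value, and both sets of results will be reported".
- **Between profiles, n ≥ 6 (steps a to e).** Values are log-transformed and the one furthest from the mean is set aside. The mean ± 3 SD of the rest is then computed. If the value set aside lies outside that range, "then it is an outlier and will be excluded from analysis". The test may be repeated while at least six values remain.
- **Reporting.** Excluded values are documented in the final report. For AUC(0-∞), a value "excluded from summary statistics will be noted in the footnote of the summary table"; half-life has a similar footnote rule. Individual values are listed (SAP 10.1), and individual derived PK parameters are reported (SAP 14.1).

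SAP 10.3.2 summarises PK parameters by treatment. It fits a power model to Cmax and AUC(0-∞) only, with 90% confidence intervals. Each of Cohorts 1 to 3 plans six participants on LY3819253 (SAP 6), so a complete dose group sits exactly at the n ≥ 6 threshold.

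**The concern.** There are three linked problems.

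First, step e is worded as an order and the preamble as a permission. The SAP does not say which prevails, so two analysts following the same text could produce different PK summaries.

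Second, the branch that applies to a full planned group is the only one of the three that does not ask for both results. Gaining or losing one evaluable value moves a group between showing both results and possibly showing only the reduced one.

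Third, the n ≥ 6 test is presented as objective, but it examines a value chosen for being extreme and measures it against an SD computed without it. At these sample sizes such a test often flags perfectly ordinary data. If flagged valid values are dropped, the reported spread is too small, and under some readings the dose-proportionality interval is too narrow.

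**Working it through.** The SAP gives no error rate for this rule, so there is no stated figure to reproduce.

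**Inputs.** Six on active per dose (SAP 6). Up to three added participants per cohort (SAP 8), so at most nine on active if all three were on active; the SAP does not give their allocation. Clean data are taken as normal on the log scale, as SAP 10.1 treats AUC and Cmax. SD is the usual sample SD. The test is applied once, within dose.

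**1. Flag rate on clean data.** For one pre-named value, the distance from the mean of the other n − 1 values, divided by their SD × √(n/(n − 1)), follows a t distribution with n − 2 degrees of freedom. The chance of exceeding 3 SD is P(|t(n−2)| > 3/√(n/(n − 1))). The rule tests whichever value is most extreme, so the group rate is at most n times this.

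| n | 3/√(n/(n−1)) | chance per value | × n | simulated |
|---|---|---|---|---|
| 6 | 2.739 | 0.0520 | 0.312 | 0.312 |
| 7 | 2.778 | 0.0390 | 0.273 | 0.273 |
| 8 | 2.806 | 0.0309 | 0.247 | 0.247 |
| 9 | 2.828 | 0.0255 | 0.229 | 0.229 |

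The simulation used 2,000,000 groups per n. A second pass cannot occur at n = 6, because only five values remain.

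**2. Effect on spread at n = 6.** Let s6 be the SD of all six log values, s5 the SD of the five that remain, and d the distance of the removed value from their mean. Then 5·s6² = 4·s5² + (5/6)·d². A flag means d > 3·s5, so 5·s6² > (4 + 7.5)·s5², and s5/s6 < √(5/11.5) = 0.66. Every exclusion therefore cuts the log SD by at least a third. In simulation the median ratio given removal is 0.56 (interquartile range 0.47 to 0.62).

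As an illustration, assume a geometric CV of 30%. The log SD is √ln(1.09) = 0.294. Multiplied by 0.56 it is 0.164, and the reported CV becomes √(exp(0.164²) − 1), about 17%.

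**3. Effect on location.** On clean data the rule is symmetric on the log scale. Simulated mean log value and mean slope differ from the truth by no more than simulation error, so geometric means and the slope are unbiased.

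**4. Effect on the power-model interval.** Doses 700, 2800 and 7000 mg, six per dose, 200,000 simulated trials:

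| Handling | slope 90% CI coverage | CI width relative to all data |
|---|---|---|
| All values kept | 90.0% | 1.00 |
| Test within every dose, every flag excluded | 83.1% | 0.93 |
| Test once on 18 pooled dose-adjusted values, every flag excluded | 90.0% | 0.97 |

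In the third row 18% of trials have a flag. If raw values were pooled without dose adjustment, and exposure were dose-proportional, the flag rate would be 0% to 1.7% for assumed CVs of 20% to 60%, so coverage would barely move.

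**The case against.** The strongest reply is that the preamble governs the whole procedure. It makes the method optional and ties exclusion to scientific judgement, so step e only classifies a value under that discretion. This is a reasonable reading, but the SAP does not state it, and it requires *will* in step e to mean *may*. It makes the conflict easy to repair but does not remove it.

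Other parts of the reply stand and limit the point:

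- A reader might infer that 31% of this trial's dose groups will lose a valid value. The documents do not support that. The procedure starts from a value already thought atypical and need not be run, so the frequency of use cannot be derived. The 31% shows how little a flag proves.
- A reader might infer that exclusions are hidden. They are not: values are listed individually and exclusions documented, so means, SDs and CVs can be recomputed. What is missing is a required parallel summary and confidence interval.
- A reader might take 83% as the coverage of the planned interval. It is an upper bound on the damage under one reading, in which within-dose exclusions carry into the power model. Pooled testing leaves coverage near 90%, and the SAP does not say which values belong to the calculation. The sentence on complete profiles may also shield AUC(0-∞).
- Day 29 concentration is not in the power model and has no planned interval, so only its spread is affected.
- The added participants serve to secure seven days of assessments, not Day 29. Without additions, one missing Day 29 sample gives n = 5, where both results are already required.

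**Conclusion.** The concern holds as a minor point. The wording of step e and the preamble conflict, and the n ≥ 6 branch alone lacks the two-result rule. Under log-normality, the usual sample SD and within-dose testing of every group, clean groups would be flagged 31% of the time at n = 6, falling to 23% at n = 9. Following step e as written would then understate SDs and geometric CVs, with a median log-SD ratio of 0.56 in an affected group of six. Within-dose testing is the natural reading for the summaries, since these are made by treatment; for the power model it is open.

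The stronger conclusions, that the PK means or slope are biased or that the planned interval will cover only 83%, do not follow. PK is a secondary objective, and the SAP sets no acceptance limit for dose proportionality, so no decision rule depends on the interval.

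**What to change.** 1. In step e, replace the order to exclude with *will be flagged for potential exclusion*, which matches the preamble.
2. For n ≥ 6, report the PK summaries and the power model with and without any flagged value, as the SAP already does for n < 6.
3. State that the test is applied within dose group, and say whether the sentence on complete profiles covers whole-profile parameters such as AUC(0-∞).

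Exclusion can stay a matter of documented scientific judgement; there is no need to limit it to proven assay, sampling or dosing errors. Nor is a new cut-off requested. Holding the clean-data flag rate at 5% for n = 6 would need about 5.3 SD, and detection of a single value shifted by 4 SD would fall from 79% to 33%.

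The cost is a few words in the SAP and one extra display when a value is flagged.
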